## Project Details

### 1. Demographics

**1.1** Project Title:  
**Implementing a Patient-Centered Intervention to Reduce Cancer Patients' Financial Toxicity**

**1.2** Short Title (required):  
**P50 I Can PIC- Aim 2**

**1.3** Project is primarily:  
**Social Science/Behavioral (includes History/Anthropology)**

**1.4** Type of Study:  
Other Interventional

**1.4.a** Is your research study one in which one or more human subjects are prospectively assigned to one or more interventions (which may include placebo or other control) to evaluate the effects of those interventions on health-related biomedical or behavioral outcomes ([NIH clinical trial definition](#)).  
**Yes**

**1.5** Select how you plan to obtain consent:

- Sign a consent document or a consent letter
- Script for use either in person or over the phone with no signature

### 2. Source(s) of Support

#### 2.1 Source(s) of Support

Type/Source	Grant Title	Name of PI on Grant	Status
Federal Agency NIH, National Cancer Institute (NCI)	Implementing a Patient-Centered Intervention to Reduce Cancer Patients' Financial Toxicity	[name]	AWARDED

## 4. Other Institutional Reviews/Requirements

**4.1** Do any of the objectives of this study involve the diagnosis, prevention, screening, evaluation, treatment or support of cancer patients?  
**Yes**

**4.2** Are more than 30% of the patients involved in this study likely to have an active cancer diagnosis?  
**Yes**

**4.11** Will a Certificate of confidentiality be used for this research?  
**Yes, certificate automatically issued by funding agency**

**4.12** Does this project need to be registered on [ClinicalTrials.gov](https://clinicaltrials.gov)?  
**Yes**

**4.12.a** Who is the Responsible Party for registering this study in ClinicalTrials.gov?  
**Principal Investigator**

**4.20** Mark all that apply to your study:

## 1. Protocol

**1.1** Is there a separate, written protocol that will be submitted in addition to this form? (Note: a grant application is not considered to be a protocol)  
**No**

**1.2** Select up to three key words below that best describe this research study:  

- **Oncology**
- **Public Health**

**1.3** Provide a short summary/abstract of the purpose and procedures of the study proposed in this IRB application.

- DO NOT include information on studies not proposed in this application.
- Use LAY terminology only. This must be easily understandable by IRB community members and nonscientists.
- DO NOT cut and paste technical abstracts from source of support applications that may not be understood by a general audience.

**The purpose of this study is to incorporate feedback from cancer patients and providers to adapt, implement, and test**

an intervention. The intervention aims to prompt screening for financial distress, facilitate discussions about care costs with cancer patients, support health insurance selection, and ultimately reduce cancer patients' financial toxicity associated with cancer care [1-3]. This intervention is an online decision tool called I Can PIC (Improving Cancer Patients' Insurance Choices).

This study will evaluate I Can PIC's impact on patient care among newly-diagnosed patients with gynecologic, colorectal, or lung cancer. At the start of Aim 2, we will conduct a historic control survey of 100 patients with newly-diagnosed gynecologic, colorectal, or lung cancer to explore whether and how treatment costs are discussed with them. We will then conduct a brief training with oncologists to talk about screening for financial distress and discussing costs with patients. The training will consist of a brief 15 min presentation delivered in-person or virtually. Next, we will conduct a pilot intervention study where patients will complete I Can PIC, then complete a survey after their next oncology appointment. 3-6 months from recruitment, patient participants will complete a follow-up survey. 3 and 6 months after beginning recruitment, we will give the providers real-time feedback about how often they screened for financial distress and referred patients to I Can PIC.

**1.4** Specify your research question(s), study aims or hypotheses:

We propose to modify the I Can PIC decision aid based on stakeholder feedback and to implement it as part of usual care, along with screening for financial toxicity and cost discussions.

The goal of this study is to evaluate the refined I Can PIC's impact on gynecologic, colorectal, and lung cancer care using a between subjects design.

**1.5** Background and significance and/or Preliminary studies related to this project:

Cancer patients often pay substantial out-of-pocket costs for care, with some spending as much as 10-20% of their annual income on healthcare expenses [4,5]. Some new cancer therapies cost thousands of dollars per month, of which a large portion can fall on patients [6,7]. In a recent study of 9.5 million cancer patients, more than 40% depleted their savings and assets within two years of diagnosis [8]. Out-of-pocket costs are rising due to longer survival times, rising prices of new cancer treatments, and insurance cost-sharing increases [5]. Financial toxicity can exacerbate health disparities; those with low income and those uninsured or underinsured have more difficulty managing the costs of cancer treatment and adhering to care plans [9, 10].

Despite patients' overwhelming concerns about care costs, providers often miss opportunities to discuss costs with them [11,12]. Although costs often impact cancer patients' treatment decisions [13], particularly when treatments lead to similar health outcomes [14], costs are not often included in patient materials. Discussing out-of-pocket expenses with patients can lower their costs without impacting cancer outcomes [15]. Yet providers often feel inadequately trained to have cost conversations. Providers often hesitate to address costs of care because costs can vary considerably across patients [11,16]. In our prior work, fewer than half of providers discussing breast cancer surgery addressed relative costs of treatment.

We also found that patients without guidance find it difficult to choose an adequate health insurance plan [17-19], particularly when viewing monthly premiums and plan features without a cost calculator. Lower health insurance literacy and suboptimal insurance led many to delay or forgo needed care [19, 20].

We developed and tested I Can PIC to help cancer patients understand insurance terms and options, consider care costs, talk to providers about financial needs, and identify financial resources or insurance to help offset care costs. I Can PIC provides plain language education at an accessible reading level, uses Medical Expenditure Panel Survey (MEPS) data to estimate annual costs patients might incur across plan types, and allows users to input their plan details to compare cost.

**1.6** Literature cited/references (if attaching a grant enter N/A):

Providers are eligible to participate in the study if they are medical or surgical oncologists who treat patients with gynecologic, lung, or colorectal cancer. The providers who will participate include: Adult (18+) patients diagnosed with first, primary gynecologic, lung, or colorectal cancer within the past 5 months, who are English-speaking will be eligible to participate. This must be a first, primary diagnosis. They must also be patients of one of the participating medical or surgical oncologists. We will exclude patients who cannot give informed consent due to cognitive or emotional barriers.

**1.8** Check all materials/methods that will be used in recruiting participants:

- Telephone script
- Ads/Brochures/Posters/News Release/Fliers
- Email or letters
- Medical Records or Other PHI

Attachment Name	Category	Version	Date Attached
I Can PIC Flyer-man.rtf	Recruitment Materials: Ads/Brochures/Posters/News Release/Fliers	2	01/08/21
P50_HC_Patient letter_102620.rtf	Recruitment: Email or letters	5	10/27/20
P50_PI_Provider Call Script_2 11 2020.rtf	Recruitment Script: Phone	1	03/04/20
P50_PI_Patient letter_102620.rtf	Recruitment: Email or letters	5	10/27/20
P50_PI_Provider screening_email_2 11 2020.rtf	Recruitment: Email or letters	1	03/04/20
P50_PI_study information sheet_patients_102620.rtf	Recruitment Materials: Ads/Brochures/Posters/News Release/Fliers	4	10/27/20
Step_1_P50_HC_Screening_script_102620.rtf	Recruitment Script: Phone	14	10/27/20
P50_HC_study information sheet_102620.rtf	Recruitment Materials: Ads/Brochures/Posters/News Release/Fliers	4	10/27/20
I Can PIC Flyer-woman.rtf	Recruitment Materials: Ads/Brochures/Posters/News Release/Fliers	2	01/08/21
P50_PI_Screening script_031221.rtf	Recruitment Script: Phone	13	03/18/21

**1.8.b** List the individual data elements you will access from the medical records (or other source of PHI) to identify potential participants for recruitment and, if applicable, any individual data elements that you will include on a screening log prior to consent.

- We will review medical records for names, age, telephone numbers, mailing addresses, language spoken at home, cancer type, date of cancer diagnosis, cancer stage, cancer treatments and completion, cancer clinician name, and cancer survivorship status from the medical record.
- In the phone screening survey we will collect age, language, cancer diagnosis, cancer type, and time since cancer diagnosis data to confirm eligibility.
- For those who choose to review the consent information sheet over the phone, we will ask for their email address after consent.

- For those who choose to review the consent information sheet online, we will ask for their email address after confirming their eligibility with the screening survey.
- On the screening log we will record age, cancer type, date of cancer diagnosis, cancer clinician name, phone number, email address (if participant gives permission), and mailing address. We will also note in the screening log if participants give us permission to email them.

**1.8.c** What is the plan for individual identifiers obtained to identify participants and, if applicable, those identifiers maintained on a screening log prior to consent?

Identifiers for those who do NOT enroll will be destroyed at the earliest opportunity, consistent with the conduct of the research (for example when recruitment and enrollment are completed.)

**1.8.d** Does the research team agree that the requested information will not be reused or disclosed to any other person or entity, except as required by law, for authorized oversight of the study, or for other research for which the use or disclosure of the requested information would be permitted by the HIPAA Privacy Rule?

Yes

**1.10** Describe where the consent discussion will occur (check all that apply):

- Private room or area
- By phone

**1.11** Participants and/or their legally authorized representative will have (check all that apply to the consent process and explain process in Question 1.12 below):

- As much time as they desire to consider enrolling in the study, including:
  - An opportunity to thoroughly review the consent materials with knowledgeable members of the research team, and with family and/or friends as appropriate
  - Sufficient time to have all of their questions answered

**1.12** Provide a description of the enrollment and consent process in sequential order and address EACH of the bulleted points below:

- Describe each study population separately including control population
- Describe when recruitment and consent materials are used
- Indicate how much time individuals will have to consider participation
- Use THIRD person active voice. For example, "the principal investigator will identify potential participants, the study coordinator will discuss the study with participants over the telephone and schedule the first study visit, etc..."
- Describe the steps that will be taken by the research team to minimize the possibility of coercion or undue influence during the consent process

For the historic control survey, the WU research staff will screen the patients of participating providers through EPIC to identify potentially eligible patients. They will retrieve the phone numbers and mailing addresses of potentially eligible patients so WU research staff can contact them. When possible based on appointments scheduled in advance (e.g., not same-day add-ons), WU research staff will mail potential participants a letter explaining the study's purpose and procedures so they have background about the study to review before being approached for consent. A week after mailing the letter, WU research staff will contact candidates by telephone to review the study and assess interest and eligibility. To confirm eligibility, WU research staff will ask for the potential participants' age, comfort reading and writing in English, cancer diagnosis, and time since cancer diagnosis.

If the potential participant is eligible and interested, WU research staff will ask if the participant would prefer to complete the survey in-person, over the phone, or online at home. If the participant chooses to complete the survey over the phone, WU research staff will review the phone consent information sheet with the participant. If the participant chooses to complete the study online, WU research staff will record their permission to send them emails, and send them a test email to confirm the email given is correct. Once staff receive confirmation from the participant they will send a link to the survey, in which the consent information is on the first page of the survey. The participant will indicate consent by clicking to the next page. If the participant chooses to complete the survey in-person, WU research staff will review the informed consent document when they meet with them in person in a private room. The potential participant can take as much time as they would like to consider their participation.

For the second part of this study, the study populations include 15 BJC medical or surgical oncologists who treat patients with gynecologic, colorectal, or lung cancer, and 80-100 of their patients who have been diagnosed with gynecologic, colorectal, and lung cancer. Participating providers will give their permission for WU research staff to review their patients' medical records and contact them about the study.

Eligible providers will be identified by the WU study team. The WU study team will contact eligible providers by phone or email to assess interest. For eligible and interested providers, WU research staff will review the consent information over the phone or send it via email (whichever the participant prefers). They will have as much time as they want to consider their participation in the study. At the time of enrollment, WU research staff will confirm participants' contact information (telephone/address/email address). Informational flyers will be distributed to participating providers to remind them of this study and the I Can PIC website and resources.

For the patient population, the WU project coordinator will screen the patients of participating providers through EPIC to identify potentially eligible patients of the participating providers. They will retrieve the phone numbers and mailing addresses of potentially eligible patients so WU research staff can contact them. When possible based on appointments

scheduled in advance (e.g., not same-day add-ons), WU research staff will mail potential participants a letter explaining the study's purpose and procedures so they have background about the study to review before being approached for consent. A week after mailing the letter, WU research staff will contact candidates by telephone to review the study and assess interest and eligibility. To confirm eligibility, WU research staff will ask for the potential participants' age, language, cancer diagnosis, and time since cancer diagnosis.

If the potential participant is eligible and interested, WU research staff will ask if the participant would prefer to complete the survey in-person, over the phone, or online at home. If the participant chooses to complete the survey over the phone, WU research staff will review the phone consent information sheet with the participant. If the participant chooses to complete the study online, WU research staff will record their permission to send them emails, send them a test email to confirm the email given is correct. Once staff receive confirmation from the participant they will send a link to the survey, in which the consent information is on the first page of the survey. The participant will indicate consent by clicking to the next page. If the participant chooses to complete the survey in-person, WU research staff will review the informed consent document when they meet with them in person in a private room. The potential participant can take as much time as they would like to consider their participation. At the time of enrollment, WU research staff will confirm participants' contact information (telephone/address/email address).

In summary this is how recruitment materials will be used:

- When possible, patient letters and study information sheets will be mailed to potential participants in the historic control and pilot intervention groups so they have background about the study to review before being approached for consent.
- Recruitment call scripts will be used to contact potential participants in the historic control and pilot intervention groups to screen them for interest in eligibility.
- The online consent information sheet will be used with those participants in the historic control and pilot intervention groups who want to complete the study online. It will be the first page of the consent.
- Phone consents will be used with those participants in the historic control and pilot intervention groups who want to complete the study over the phone.
- Informed consents with PHI information will be used with those participants in the historic control and pilot intervention groups who want to complete the study in-person.

**1.13** Provide a detailed description in sequential order of the study procedures following the consent process - DO NOT cut and paste from the Consent Document.

Describe study populations separately if they will be participating in different procedures

DESCRIBE:

- Control populations, if applicable
- Any randomization, if applicable
- What participants will be asked to do/what happens in the study (in sequential order)
- The time period over which procedures will occur
- Long-term follow-up and how it occurs

At the start of this study, we will conduct a historic control survey of 100 recently diagnosed gynecologic, colorectal, and lung cancer patients. They can complete the survey in-person, over the phone, or online. The survey will take approximately 15 minutes to complete. It will ask about their knowledge of health insurance and confidence communicating about care costs. WU research staff will collect participants' distress assessment data, insurance status and other health conditions data from the electronic medical record in EPIC. At the time of enrollment, WU research staff will confirm participants' contact information (telephone/address). If they give us permission to email them we will document this in our records. They will receive a \$10 gift card as a thank you for their time.

Then, we will train 15 BJC gynecologic, colorectal, and lung cancer care providers in using I Can PIC and discussing costs with patients in a brief 15 min presentation that can be delivered in-person or virtually. Providers will complete a survey before and after their brief training at the start of the study. These surveys will take approximately 5-10 mins to complete in total. During the study, at 3- and 6- months, we will give providers on the percent of time that they screened for financial distress and referred patients to I Can PIC. This information is collected from the patient participants' surveys. At the end of the study, we will examine adoption, implementation, and maintenance measures. Providers will receive a \$50 gift card at the end of the study.

Next, we will recruit 100 gynecologic, colorectal, and lung cancer patients of the providers we trained over a 9 month period. At the time of enrollment, WU research staff will confirm participants' contact information (telephone/address). If they give us permission to email them we will document this in our records. Next, they will use I Can PIC. This will take approximately 10-15 mins. After their next appointment with their provider, they will complete a brief survey online about their knowledge of health insurance and confidence communicating about care costs. WU research staff will provide their survey to participants via phone, email, or in-person. The survey will take about 10 mins. Participants will receive a \$20 gift card for reviewing I Can PIC and completing the survey.

Patient participants who choose to complete the study in person may view I Can PIC on a tablet provided by us in the clinic or at our office. Then after their appointment, they can complete the survey on a tablet provided by us in the clinic or at our office. If they choose to complete it over the phone, we will email them the link to I Can PIC and then call them when it is time to complete the survey. If they wish to complete it online, we will email them the link to I Can PIC, and then the survey after their appointment. WU research staff will collect participants' distress assessment data, insurance status and other health conditions data from the electronic medical record in EPIC. After 3-6 months, participants will receive a follow-up survey which they can complete in-person, online, or over the phone. WU research staff will collect participants' distress assessment data, insurance status and other health conditions data from the electronic medical record in EPIC. This survey will take about 10 mins to complete. Once it is done, we will mail them a \$10 gift card.

**1.14** Will participants be randomized?

No

**1.15** Will any of the following be used to collect information from the participant or others?

- Screening questions or screening/eligibility questionnaires
- Surveys
- Questionnaires
- Stimuli
- Any other written assessments

Yes

Attachment Name	Category	Version	Date Attached
P50_PI_post-intervention_survey_patients_05_20_2020.docx	Subject Data Collection Instruments	5	05/20/20
P50_PI_3-6 month follow-up_survey_patients_05_20_2020.docx	Subject Data Collection Instruments	6	05/20/20
P50_PI_Screening_Survey_031121.docx	Subject Data Collection Instruments	3	03/18/21
P50_PI_pre_training_survey_for_providers_2_28_2020.docx	Subject Data Collection Instruments	1	03/04/20
P50_HC_historic_control_survey_05_20_2020_v2.docx	Subject Data Collection Instruments	5	05/20/20
P50_PI_follow-up_survey_for_providers_2_28_2020.docx	Subject Data Collection Instruments	1	03/04/20

**1.16** Does this project involve creating any audio, video, or photographs?

No

**1.17** Does the study include any form of deception (e.g., providing participants with false information, misleading information, or withholding information about certain study procedures)?

Examples:

- Procedure includes a cover story that provides a plausible but inaccurate account of the purposes of the research.
- Participants will be provided with false information regarding the particular behaviors of interest in the research.
- Procedures include a confederate pretending to be another participant in the study.
- Participants will be told that the research includes completion of a particular task, when in fact, that task will not be administered.
- Study is designed to introduce a new procedure (or task) that participants are not initially told about.

No

**1.18** Indicate any payments or reimbursements to participants (check all that apply)

- [Gift or Debit Card](#)

**1.19** Does this study have a plan to have an individual or committee review combined data from all participants on a periodic basis (such as summary or aggregate safety and/or efficacy data)?

No

**1.20** What have you done to minimize any risks?

- No foreseeable risks

**1.21** What are the potential benefits related to this project for:

- the participant (if any)
- benefits to society (if any)

There are no direct benefits to participation. Our goal is that the knowledge gained will benefit cancer patients and survivors in the future who are managing health care costs. Participants may feel a sense of contribution to their community and to others. They could also learn about health insurance terminology and care costs resources through participating in the study.

The results of this study will inform efforts to implement I Can PIC in a hospital system. Given that risks to participants are minimal, they do not outweigh these potential benefits.

**1.22** Provide a summary of the analysis methods you will use, including, if applicable, the data points or outcomes you will analyze.

Descriptive statistics will be calculated for all variables and RE-AIM outcomes. Data will be examined for effectiveness outcomes between historic controls and intervention groups in a multivariable regression model controlling for up to 4 independent covariates (e.g. age, health literacy, insurance status, cancer type). The 3-6

month follow-up survey will be also conducted for the intervention group. The change in patient's outcomes between the first time point (after viewing I Can PIC) and the 3-6 month follow-up will be examined in a multivariable regression model controlling for up to 4 independent covariates (e.g. age, health literacy, insurance status, cancer type). We will examine the change in clinicians' responses to the surveys at the first time point and at the completion of the study in a regression model.

**1.23** Provide the rationale or power analysis to support the number of participants proposed to complete this study.  
All outcomes of patient participants are measured at screening for historic controls and at post-intervention for intervention groups. Power estimates are dependent on the effect size of each outcome, defined as the mean difference between two groups divided by the standard deviation. Using a two-tailed two-group t-test, a sample size of 80 patients with newly diagnosed breast, lung, or colorectal cancer in the intervention group and 80 historic controls has at least 80% power to detect an effect size of as small as 0.45 at a 0.05 level of significance. We will recruit up to 100 patients in each group (intervention and historic control) since we expect that some patients will drop out/not complete the surveys or follow-up. Powers were calculated using Power Analysis and Sample Size (PASS 15) software.

**1.25** Will any data from this project be stored for use in future research studies?  
No

**1.26** Does this project involve the collection or use of biological samples or genetic data?  
No

**1.27** Are you requesting institutional certification to contribute human data or samples to a repository or database for broad sharing (public or restricted access)?  
No

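### Does the missing reference date for insurance status, a possible adjuster, undermine the comparison of I Can PIC patients with historic controls?

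*Combined protocol and SAP*

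**What the plan says.** Section 1.22 sets out a regression comparing historic controls with "intervention groups in a multivariable regression model controlling for up to 4 independent covariates (e.g. age, health literacy, insurance status, cancer type"). The same example list is repeated for a second model, restricted to patients who received the tool: "The change in patient's outcomes between the first time point (after viewing I Can PIC) and the 3-6 month follow-up will be examined".

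Section 1.13 describes where insurance status comes from.

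- **Controls:** one extraction, where the text runs "distress assessment data, insurance status and other health conditions data from the electronic medical record in EPIC. At the time of enrollment".
- **Intervention patients, first extraction:** described after tool use and the post-visit survey, where the text runs "insurance status and other health conditions data from the electronic medical record in EPIC. After 3-6 months, participants will receive a follow-up survey".
- **Intervention patients, second extraction:** placed inside the description of the follow-up survey, where the text runs "insurance status and other health conditions data from the electronic medical record in EPIC. This survey will take about 10 mins to complete".

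No extraction carries a reference date, and section 1.22 does not say which value enters either model.

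Insurance is also something the tool tries to influence. Section 1.3 says it should "support health insurance selection", and section 1.5 says it helps patients "identify financial resources or insurance to help offset care costs".

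Health literacy is named as a covariate only in section 1.22. The screening items in section 1.8.b are "age, language, cancer diagnosis, cancer type, and time since cancer diagnosis data to confirm eligibility"; health literacy is not among them.

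**The concern.** The groups are not randomized (section 1.14), so regression adjustment is the only stated control for differences between them. Adjusters should be fixed before exposure. If insurance status were read after a patient had used the tool, and the tool had led that patient to change cover, adjusting for it would remove the part of the effect that runs through insurance. Controls never see the tool, so the distortion would be one-sided. It would pull the estimate toward zero if the insurance changes improved the outcome, and push it away if they worsened it.

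With one undated value in one group and two in the other, the adjusted result appears to hang on an analyst's choice. Health literacy raises the same question if intervention patients are first asked about it after using the tool.

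**Working it through.** **1. The plan's own figure.** Section 1.23 gives 80 per group, a standardized difference of 0.45, two-sided 5% and at least 80% power. The normal approximation gives 81.2% and the exact t calculation 80.8%. The size needed for 80% power is 78 (normal) or 79 (t) per group. The stated figure reproduces, and covariate timing does not alter it.

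**2. Which extraction goes with which outcome.** Section 1.23 says intervention outcomes for the comparison are taken post-intervention. In section 1.13 the first extraction follows the post-visit survey and comes before the 3-6 month step; the second belongs to the follow-up survey. The natural pairing for the between-group model is therefore the first. For controls there is one survey, one extraction and no exposure, so no date could let a tool effect in. What stays open is whether the first intervention value reflects cover before or after tool use. The order of sentences does not settle this: in the control paragraph, the extraction is also described before the enrolment step.

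**3. How much tool-driven change would matter.** Take a binary insurance category, outcome SD of 1 within group and category, category difference g, and net share p of intervention patients moved by the tool before the recorded date. Then

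adjusted effect = 0.45 − g × p.

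A 10% shift means g × p = 0.045, giving an effect of 0.405.

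| g (assumed) | p = 0.045 / g | Patients out of 80 |
|---|---|---|
| 0.3 | 15% | 12 |
| 0.5 | 9% | 7.2 |

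A simulation with 80 per group, 4,000 runs and 50% in each category gave mean adjusted effects of 0.404 and 0.405 at these two points, and 0.448 and 0.451 with p = 0.

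**4. A second illustration.** Assume 80% are adequately insured at the start and the tool moves 5 to 15 percentage points of all intervention patients into adequate cover, with g again 0.3 to 0.5. Adjusting for the pre-tool value recovers about 0.45 throughout. Adjusting for the post-tool value gives 0.435 at the mild end (5 points, g = 0.3) and 0.376 at the severe end (15 points, g = 0.5). Power at those effects is 78.0% and 65.6%.

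Under this assumption 0.20 × 80 = 16 intervention patients start without adequate cover. Moving 15 points means 0.15 × 80 = 12 of those 16, or 75%. Even 5 points means 4 of 16, or 25%. For the between-group model, this would have to happen and be recorded between tool use and the early extraction.

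**5. The 3-6 month model.** Two insurance values exist here, so the choice is more open. There is no comparator, however, so no between-group effect is at risk. If the model is a linear regression of change scores with centred covariates, fitted to the same patients, its intercept equals the sample mean change whichever insurance value is entered. Only the covariate coefficients and the precision differ.

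**The case for a change.** The strongest case for acting is that the factual points are all correct: one extraction against two, no dates, a tool that aims at insurance choice, and an adjuster with no stated timing in a non-randomized comparison. The first intervention extraction is described after tool use, so a post-exposure value is not ruled out. The severe corner of the illustration is not trivial, and dating the covariate at enrolment would cost a sentence, since the record is being read anyway.

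The description of the gap stands; the consequence does not. Harm needs four things together: insurance status is among the covariates chosen, its value post-dates tool use, the tool has changed recorded cover by then, and that change moves the outcome. The documents establish none of them. The survey content described in section 1.13 is insurance knowledge and confidence in raising costs, and no passage says that insurance category drives either. The values of g, p and starting prevalence in the illustrations are all assumed.

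The health literacy point cannot be judged from these documents. The screening, post-visit and control surveys are listed as attachments (section 1.15) whose content is not shown, and the section 1.8.b list covers eligibility items, not necessarily everything asked. It is a question for the investigators. The missing comparator at 3-6 months is a separate matter: section 1.22 presents that analysis as a change from a post-tool starting point and makes no claim of effect from it.

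**Conclusion.** No change to the plan is called for. The reference date is a missing detail, and ordinary practice fills it: an analyst adjusting a post-visit outcome would use the early insurance value, read as near enrolment as the record allows, and leave the follow-up value for description. No rule stated in section 1.22 produces a wrong result, and no stated number changes.

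Any bias in the between-group estimate is zero if the tool moves nobody's recorded insurance before the early extraction. It stays under a tenth of the planned 0.45 SD effect unless about 7 to 12 of 80 intervention patients change category because of the tool in that interval. That range assumes a binary category and a 0.3 to 0.5 SD outcome difference between categories, neither of which is in the documents. Confidence is high on the counts and on the absence of dates. The judgement that the consequence is small rests on the short interval before the next visit and on the lack of evidence that cover changes within it.
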